7. ANALYSIS POPULATIONS

7.1. Intent-To-Treat (ITT) Population

The “Intent-to-Treat (ITT) Population” comprises all randomized patients, regardless of whether or not study drug was administered. This population will serve as the primary population for the analysis of the efficacy data. All analyses using this population will be based on the treatment assigned by IXRS.

7.2. As-Treated (AT) Population (Safety Population)

The “As-Treated (AT) Population” is defined as all subjects who receive at least one dose of study medication. This population will be used in the assessment and reporting of safety data. The “As-Treated Population” is equivalent to “Safety Population”. This population will be used for safety analyses. All analyses using this population will be based on the treatment actually received.

7.3. Tumor Response(TR) Population

The “Tumor Response (TR) Population” will include all patients in the ITT population that meet both of the two following criteria:

1. Subject has measurable disease (at least one target lesion) at baseline;
2. Subject has at least one post-baseline evaluation or early disease progression/cancer-related death occurred before first evaluation on treatment (post-baseline) took place.

All analyses using this population will be based on the treatment assigned by IXRS.

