	 As-Treated (AT) population: This population includes all patients who took part of any dose of study treatment. This population is for safety analyses. All analyses using this population will be based on the treatment actually received.
	• Tumor Response (TR) Population: All patients in the ITT population with measurable disease (at least one target lesion) at baseline and with at least one tumor evaluation while on treatment. (Patients who have disease progression or a cancer-related death prior to their first on treatment tumor evaluation will also be considered evaluable.) All analyses using this population will be based on the treatment assigned by IXRS.
	Primary Efficacy Endpoint (OS)
	OS is defined as the time from the date of randomization to the date of death. If death is not observed during the study, the time will be censored at the last date patient is known to be alive or the cut-off date, whichever is earlier. For the primary analysis of OS, the two treatment arms will be compared using the stratified log-rank test using the 3 stratification factors in the randomization as per IXRS assignment. The hazard ratio (HR) will be estimated, along with the associated 2-

	sided 95% confidence intervals (CI), using a stratified Cox's proportional hazard (CPH) model. Survival for each arm will be summarized using Kaplan Meier curves and further characterized in terms of the median and survival probability at 3, 6, 9 and 12 months, along with the corresponding 2-sided 95% CI for the estimates.
Statistical Methods	Key Secondary Efficacy Endpoint (PFS)
(continued):	PFS will be evaluated from date of randomization to the first occurrence of radiologic progression or death. Treatment comparisons for PFS will use similar analytical methods as the OS endpoint.
	Other Secondary Efficacy Endpoints

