12.1.3. Reporting of Deaths

All deaths occurring through the 30-day follow-up period must be reported in the eCRF within 24 hours.

1. Death due to disease progression:

Disease progression (radiologic or clinical) with the outcome of death will not be reported as an SAE. However, relevant signs, symptoms and complications of disease progression (radiologic or clinical) must be reported as an AE or SAE if it meets the serious criteria. It should be indicated that the signs, symptoms and complications are related to disease progression.

2. Death due to other causes:

Deaths due to reasons other than disease progression must be reported as an SAE.

Death is not an acceptable AE/SAE term. Death is an outcome of an SAE.

When reporting a death in the eCRF, you will be required to identify which of the following best describes the category of death:

- Toxicity for study drug
- Radiologic disease progression
- Clinical disease progression
- Other causes

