13.1. Study Populations

The safety and efficacy study populations will be defined as follows:

- Intent-to-Treat (ITT) population: This population includes all randomized patients and is the primary population for all efficacy parameters. All analyses using this population will be based on the treatment assigned by IXRS.
- As-Treated (AT) population: This population includes all patients who took part of any dose of the study treatment. This population will be used for safety analyses. All analyses using this population will be based on the treatment actually received.
- Tumor Response (TR) evaluable population: This population includes all patients in the ITT population with measurable disease (at least one target lesion) at baseline and with at least one tumor evaluation while on treatment (except for early disease progression/cancer-related death). All analyses using this population will be based on the treatment assigned by IXRS.

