3.2.3.1. Overall Response Rate

The assessment of ORR will be based on Investigator review of radiologic images and following RECIST criteria (version 1.1 2009). ORR is defined as the proportion of patients with objective evidence of CR or PR. The primary assessment of ORR will be in the ITT population, restricted to patients with measurable disease (at least 1 target lesion) at Baseline.

At the analysis stage, the best overall response will be assigned for each patient as the best response recorded from all responses recorded from the start of treatment through the treatment period (excludes assessments during follow-up). If applicable, responses recorded after radiologic disease progression or initiation of non-study antitumor therapy will be excluded. A patient's best response assignment of SD needs to be maintained for at least 6 weeks from the start of treatment.

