10.4.4.1. ORR

Overall response rate (ORR) is defined as the proportion of patients with objective evidence of CR or PR. The treatment comparison for ORR will be based on the TR population using Fisher's exact test in the subset of patients in the Intent-to-treat population with measurable disease at baseline (TR population). Treatment estimates and differences will be presented along with the associated 2-sided 95% CIs constructed using the Clopper-Pearson approximation to the exact binomial proportion [17] for individual estimates within group; and the normal approximation for the difference between groups.

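### The Tumor Response rule drops unscanned patients from the ORR and DCR tests according to attributed cause of death, and conflicts with the ITT measurable-disease denominator in SAP 3.2.3.1

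*SAP*

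**What the plan says.** Besides measurable disease at baseline, SAP 7.3 requires that "Subject has at least one post-baseline evaluation or early disease progression/cancer-related death occurred before first evaluation on treatment (post-baseline) took place". Protocol 13.1 has the same exception but ties the scan to treatment: "at least one tumor evaluation while on treatment (except for early disease progression/cancer-related death". The protocol synopsis reads "Patients who have disease progression or a cancer-related death prior to their first on treatment tumor evaluation will also be considered evaluable", and the SAP synopsis agrees with it.

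On the analysis set the documents disagree:

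- SAP 10.4.4.1: "The treatment comparison for ORR will be based on the TR population". The same sentence goes on to describe that set as patients "in the subset of patients in the Intent-to-treat population with measurable disease at baseline (TR population". SAP 10.4.4.2 applies the same method to DCR, and protocol 13.3.2.3 also names TR for both endpoints.
- SAP 3.2.3.1: "The primary assessment of ORR will be in the ITT population, restricted to patients with measurable disease (at least 1 target lesion) at Baseline". SAP 3.2.3.2 makes DCR parallel to ORR.
- Protocol 13.1 names ITT as the primary population for every efficacy parameter.

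Protocol 12.1.3 has the site classify each death, and "Toxicity for study drug" is a category separate from radiologic progression, clinical progression and other causes. SAP 8.13.1 imputes no missing efficacy data unless otherwise specified. No sentence says explicitly that an unscanned patient counts as a non-responder.

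**The concern.** Take two measurable-disease patients who both die in week 5, unscanned and without recorded progression. If one death is attributed to the cancer, that patient stays in TR as a failure. If the other is attributed to toxicity or another cause, that patient disappears from the denominator. A patient who stops for intolerance and is never scanned also disappears, as does one who is randomized but never dosed (a group that protocol 8.4.2 recognises). None of these patients has shown a response or disease control, and all are lost through events after randomization. The comparison is then no longer between the groups as randomized, and membership depends partly on an investigator's attribution.

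At stake are the ORR and DCR estimates and their Fisher p-values, which belong to a SAP written to support a marketing application. The conflict over the denominator also leaves a choice between two sets that can give different answers.

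**Working it through.** **1. The two sets compared.** SAP 3.2.3.1 requires a target lesion at baseline and nothing more. SAP 7.3 adds a second condition. TR is therefore a subset of the SAP 3.2.3.1 set, and the two coincide only if no measurable-disease patient lacks both a scan and a qualifying event. The equation of the two in SAP 10.4.4.1 is not correct in general.

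**2. The plan's own figures.** The documents give no power or sample size for ORR or DCR. The survival inputs used below (control median about 5 months, HR 0.70, 2:1 allocation; SAP 4.3.1) are consistent with the plan: 384 deaths give 90.9% power by the Schoenfeld formula at 1-sided 0.025, against the stated 90%. The Phase 2 gastric DCR of 65.5% (45.7, 82.1) reproduces as 19/29 with an exact interval.

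**3. How many patients could be unscanned.** The first on-treatment scan is at 8 weeks: 56/30.4375 = 1.84 months. With exponential survival:

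- placebo: 1 − exp(−(ln 2/5) × 1.84) = 22.5%
- TAS-102: 1 − exp(−0.70 × (ln 2/5) × 1.84) = 16.4%

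These are deaths from all causes. Only those without a scan, without early progression and not attributed to cancer are dropped.

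**4. Effect on a rate.** If a share d of an arm is dropped and all of them are failures, the rate becomes rate/(1 − d): ×1.01 at 1%, ×1.05 at 5%, ×1.11 at 10%.

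**5. Size of the shift.** The documents give neither the measurable-disease share nor non-cancer early-death rates by arm, so these are assumptions: 290 v 145 measurable patients, and DCR 40% v 15% (116 and 21.75 patients) when all are counted. Early deaths are 0.164 × 290 = 47 and 0.225 × 145 = 33.

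| Assumption | Dropped (TAS-102 v placebo) | DCR in TR | Difference (full set 25.0) |
|---|---|---|---|
| Low: 10% v 5% of early deaths not cancer-related | 4.7 v 1.6 | 116/285.3 = 40.7%; 21.75/143.4 = 15.2% | 25.5 |
| High: 30% v 10% | 14.2 v 3.3 | 116/275.8 = 42.1%; 21.75/141.7 = 15.4% | 26.7 |
| Low, plus 3% v 1% unscanned withdrawals | 13.4 v 3.1 | 41.9%; 15.3% | 26.6 |
| High, plus 6% v 3% | 31.6 v 7.7 | 44.9%; 15.8% | 29.1 |

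A higher base rate scales the shift. With 300 v 150 patients and DCR 65.3% v 14.7%, the difference goes from 50.7 to 51.3 points at 1% v 0% dropped and to 54.1 at 5% v 0%.

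**6. Direction.** In every row above the larger TAS-102 loss is an input. If 2% v 6% are dropped instead, 40/0.98 − 15/0.94 = 40.8 − 16.0 = 24.9 points, slightly against TAS-102. For small losses the break-even is a placebo share about 40/15 = 2.7 times the TAS-102 share.

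**7. Whether a p-value could move** (300 v 150, Fisher):

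- DCR 30% v 22%: p = 0.074 on the full set, 0.044 at 5% v 0% dropped, 0.056 at 5% v 2%, and 0.14 at 5% v 10%.
- ORR 5% v 2%: the difference goes from 3.0 to 3.1–3.4 points where TAS-102 loses the larger share, and p from 0.20 to 0.13–0.14.

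**The case against.** The strongest reply is that SAP 3.2.3.1 already names all measurable-disease ITT patients as the primary set, and that set drops nobody. If it governs, TR is only a secondary view. This stands in part: a reader might infer that early failures leave every ORR and DCR denominator, and the documents do not support that. But protocol 13.3.2.3 and SAP 10.4.4.1–10.4.4.2 assign the tests to TR, so SAP 3.2.3.1 shows a contradiction and does not cure the rule.

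A reader might also infer that the rule must favour TAS-102. Toxic deaths and toxicity stops should fall mainly there, but that is inference. The Phase 2 gastric study reports no treatment-related deaths among 29 patients (exact 95% upper limit 1 − 0.025^(1/29) = 11.9%), and the Phase 3 colorectal study reports one. Neither shows a material excess, and the Phase 2 figure cannot exclude one. SAP 7.3 does not say whether clinical progression without a scan is early progression; protocol 8.5.1 lists clinical progression separately from RECIST progression. If it does not count, placebo could lose more patients.

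The withdrawal rows are the weakest. The Phase 2 figure of 6.9% (2/29) counts stops for adverse events at any time, scanned or not. Protocol 10.1.13 continues 8-weekly scans after a stop without radiologic progression, and under the SAP 7.3 wording a scan after stopping keeps the patient in TR. The unscanned group is probably smaller than 3–6%. It need not be empty: the scan before new therapy is on a best-effort basis, and protocol 10.2.6 can waive the End of Treatment visit.

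**Conclusion.** The point holds as a defect of definition and an unresolved contradiction. The TR rule removes randomized failures from a planned test according to attributed cause of death, and the SAP names two different denominators as if they were one. Removing failures can only raise an arm's rate; which arm gains more cannot be settled from the documents.

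The likely effect is small: about 0.5 point on the DCR difference under the low-end assumptions, which the few reported toxic deaths make more plausible than the high end. Larger shifts, up to the 29.1-point difference in the last table row, need unscanned withdrawals to be common and concentrated on TAS-102. The effect on the ORR difference is a few tenths of a point. A DCR test could cross 0.05 only if it were already close.

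ORR and DCR are other secondary endpoints without multiplicity control, and OS and PFS do not use TR. The change is still worth making, because it is cheap and removes both the selection and the ambiguity.

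**What to change.** In SAP 7.3, 10.4.4.1 and 10.4.4.2, protocol 13.1 and 13.3.2.3, and both synopses:

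- Make all ITT patients with measurable disease at baseline, the SAP 3.2.3.1 set, the single denominator for the ORR and DCR tests, and remove the wording that equates it with TR.
- State that every patient in that set with no post-baseline tumor evaluation, whatever the reason (death from any cause, early withdrawal or never being dosed), counts as a non-responder without disease control.
- Keep the present TR set as a sensitivity analysis, and tabulate its exclusions by arm and reason.

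The cost is a text change and slightly lower reported rates. No new data are needed, and SAP section 2 allows such decisions up to database freeze.

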8. DERIVED AND TRANSFORMED DATA

8.1. Age (relatively to Informed Consent Date)

Subject's age in years (whole number, no decimals) will be calculated using date of informed consent (IC) as the reference point. An appropriate SAS expression recommended by SAS Institute for calculation of a correct age of a person will be applied to calculate the age. The expression is supposed to take into account leap years and other peculiarities of the Gregorian calendar. The formula reads as follows:

Age (year) = INT(INTCK("MONTH", date of informed consent – date of birth)/12)

IF MONTH(date of birth) = MONTH(date of informed consent)

THEN Age = Age - (DAY(date of birth) > DAY(date of informed consent));

where INT() function (SAS) returns the integer part of the result, INTCK("MONTH", DATE2 – DATE1) function (SAS) returns a number of months between DATE1 and DATE2, MONTH() and DAY() – standard SAS functions returning month and day of the month of the argument, correspondingly.

8.2. Study Day

If the date of interest occurs on or after the first dose/randomization date then study day will be calculated as (date of interest – date of first dose/randomization) + 1. If the date of interest occurs prior to the first dose/randomization date then study day will be calculated as (date of interest – date of first dose/randomization). If the date of the first dose is different from the date of randomization (protocol allows 3 day window between randomization and start of the treatment), the date of the first dose will be used in the aforementioned calculations. There will be no study day 0.

8.3. Baseline

Baseline assessment is defined as the last valid/non-missing measurement obtained prior to administration of the first dose of study medication. If the time of the medication and/or time of the assessment is not available, baseline is defined as last valid measurement obtained prior to or on the date of administration of the first dose of study medication

If the multiple results are available that were obtained at the same date and there is no reasonable way to uncover their chronological order, the average value will be used as a baseline (for continuous variables).

All recorded valid data will be considered for analysis of baseline values (including test performed at unscheduled visits).

8.4. Change from Baseline

Change from baseline is calculated as (post-baseline result – baseline result).

Percent change from baseline is calculated as (change from baseline/baseline result * 100).

If either the baseline or the post-baseline result is missing, the change from baseline and/or percentage change from baseline is set to missing as well.

8.5. Day 1

The date of first administration of study medication (first dosing) is defined as Day 1 of treatment (D1). The date of first administration of study medication (first dosing) within the Cycle N is defined as Day 1 of the Cycle N (CND1).

8.6. End of Study

The final data cut off will be defined by the date of the 384th death. All patients dying on the calendar date of the 384th death will be included in the analysis should more than one patient die on the calendar date of the 384th death. Subjects that will be alive on the calendar date of the 384th death will be considered as ongoing study.

8.7. Visit Windows

Windows mentioned in the protocol of the present study are used for operational purposes only and they will not be utilized for any analysis.

For the purpose of analysis lab tests, vital examinations, ECOG performance status, tumor assessments, etc. will be assigned to an appropriate cycle according to the start date of this cycle and the start date of the next one. In general, Cycle N will be defined as all days starting with Day 2 of the Cycle N until the Day 1 (including) of the Cycle (N+1). Detailed instructions how an assignment should be performed will be presented in the **CCI** (“Data Handling Guidance”).

For the purpose of presentation of AE and/or CM in the listings an assignment to the appropriate cycle will be performed. In general, Cycle N will be defined as all days starting with Day 1 of the Cycle N till the day (including) before Day 1 of the Cycle (N+1). For the last cycle a standard 30 days window after the last dose will be applied. Detailed instructions how an assignment should be performed will be presented in the **CCI** (“Data Handling Guidance”).

8.8. Multiple Assessments

When valid multiple assessments within the same cycle (refer to) are available their presentation will depend on the specific output. Detailed instruction for analysis will be presented in and in the “Data Handling Guidance”).

8.9. Time Adjusted Incident Rate (per 100 Subject Year)

The incidence rate (per 100 patient year) of a given event/TEAE is defined as the number of patients experiencing the event/TEAE during time at risk divided by the total time of patients at risk to contribute an event to the analysis multiplied by 100 (per 100 patient year).

Here Time at risk [patient years] = (date of first onset of event/TEAE - study drug start date + 1)/365.25. If the event/TEAE of interest did not occur for a patient, time at risk will be censored at the end of the event/TEAE period, which is defined in [Section 11.1.2](#)

8.10. Days to “Recovery” (Grade 3 or Grade 4 abnormalities)

The number of days to “recovery” for the Grade 3 or Grade 4 abnormalities (that worsen from baseline or had missing baseline) in clinical lab tests for a subject is defined as the number of days from the moment when this abnormality is recorded for the first time until the time (subsequent event) when CTCAE grade for this test is reduced to a value 2 or 1. If the test continues to demonstrate the same (or higher) CTCAE grade (i.e., Grade 3 or Grade 4) continuing to the end of the study or the subject’s death (whichever occurs earlier), the duration is censored at either the end of the study or the subject’s death as appropriate.

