9.2.4.3. Dose Modification in Response to Hematologic Toxicities

Criteria for dose hold and resumption in response to hematologic toxicities related to myelosuppression are described in Table 5 and Table 6, respectively.

NOTE: For all patients with decreases in neutrophils and/or platelets, the next cycle of study treatment should not be started until the resumption criteria in Table 6 are met; these resumption criteria apply to the start of the next cycle for all patients regardless of whether or not the hold criteria were met.

Table 5: TAS-102 Dose Hold Criteria for Hematologic Toxicities Related to Myelosuppression

	Hold Criteria		
Parameter	Conventional Units	SI Units	
Neutrophils	<500/mm ³	$<0.5 \times 10^9/L$	
Platelets	<50,000/mm ³	$<50 \times 10^{9}/L$	

SI=International System

Table 6: TAS-102 Resumption Criteria for Hematologic Toxicities Related to Myelosuppression

	Resumption Criteria ^a		
Parameter	Conventional Units	SI Units	
Neutrophils	≥1500/mm ³	$\geq 1.5 \times 10^{9}/L$	
Platelets	≥75,000/mm ³	≥75 × 10 ⁹ /L	

^a These resumption criteria apply to the start of the next cycle for all patients regardless of whether or not the hold criteria were met.

SI=International System

Criteria for dose reduction in response to hematologic toxicities are as follows:

- Uncomplicated neutropenia or thrombocytopenia ≤Grade 3 do not require a reduction in dose of study medication.
- Patients who experience uncomplicated Grade 4 neutropenia or thrombocytopenia that results in a ≤1 week delay of the start of the next cycle should start the next cycle at the same dose level.
- Patients who experience uncomplicated Grade 4 neutropenia or thrombocytopenia that results in a >1 week delay of the start of the next cycle should start the next cycle at one reduced dose level as described in Table 3.

Patients who experience complicated ≥Grade 3 neutropenia or thrombocytopenia should be considered for administration of hematopoietic growth factors, or for a dose reduction in the next cycle or both, dependent on the severity of the complication.

In the event of febrile neutropenia:

- Interrupt dosing until toxicity resolves to Grade 1 or baseline
- When resuming dosing, decrease the dose level by 5 mg/m²/dose from the previous dose level (as per Table 3).

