10.1.10. Clinical Laboratory Evaluations

10.1.10.1. Hematology

Collect blood for hematological assessments at the following time points and when clinically indicated:

- Within 7 days prior to Day 1 of Cycle 1 (Laboratory results obtained prior to signing ICF may be used if the results were obtained within 7 days prior to Day 1 of Cycle 1.)
- Day 15 of Cycle 1
- Beginning with Cycle 2, obtain within 24 hours prior to start of study treatment in every cycle

- End of Treatment Visit (if applicable)
- 30-day Safety Follow-up Visit

In addition, follow the criteria for repeat testing listed in Section 12.2.2 as needed.

Measure the following hematology parameters:

Red blood cell (RBC) count	White blood cell (WBC) count with differential (automated):
Hemoglobin	Neutrophils
Hematocrit	Lymphocytes
Platelets	Monocytes
	Eosinophils
	Basophils

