10.2.8. Survival Follow-up after 30-Day Safety Visit

The following assessments should be obtained at scheduled 4-week (± 7 days) time intervals during the survival follow-up period:

- Tumor measurement (by CT scan, see Section 11) every 8 weeks until radiologic disease progression (for patients who discontinued treatment for reasons other than disease progression) or initiation of new anticancer therapy (whichever occurs first)
- Concomitant medications collect antitumor therapies only
- Contact patient/caregiver to determine survival status (alive/dead)
- SAE collection only if the SAE is related to study medication

Patients will be followed for survival until the target number of events is reached. The Investigators will be informed when this target is reached.

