11.6. Clinical Laboratory Data

All laboratory values will be converted to SI units and classified as normal, low, or high based on normal ranges (converted to SI units if needed) supplied by the laboratory performed the test. Laboratory categories will be expressed in terms of the L (below LLN), N (between LLN and ULN) and H (above ULN) classifications for numerical measurements and normal, abnormal for characteristic measurements. Additionally, abnormal laboratory values will be presented according to the NCI CTCAE v4.3 laboratory toxicity grades. All laboratory data will be coded with CTCAE grade, where CTCAE grading is available. Local laboratory ranges will be used for grading. In the event a range is not available a standard set of lab ranges as detailed in **CCI** will be utilized and flagged in the database.

Tables of descriptive statistics for hematology, biochemistry and urinalysis will be presented. Summary statistics (descriptive statistics) for quantitative laboratory parameters will include number of subjects, mean, standard deviation, median, minimum and maximum. Continuous parameters will be summarized for the actual and change from baseline values for all available parameters and study visit time points. Categorical results will be represented by shift tables (by visit) for the tests where NCI CTCAE grading is not available.

Changes in the NCI CTCAE grade from baseline to the worst grade recorded post-baseline will be tabulated in the form of shift tables. Applicable bi-directional laboratory tests will be represented as one artificial one-directional tests, where hypo- part (below the LLN) will be assigned with negative signs and hyper- part (above the ULN) will continue to keep positive values. Therefore, valid grades for this artificial test will cover span from -4 to +4, where Grade 0 will correspond to

the values lying within the normal range. The definition of hypo- and hyper-toxicity grades follows the definition provided by the NCI CTCAE v4.3 definition document. Laboratory tables with CTCAE grading will only be produced for laboratory parameters for which CTCAE grading is available. An overall shift summary will also be provided comparing baseline to worst post-dose toxicity observed across all visits.

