11.6.1. Hematology

The following test will be summarized and tabulated, all other hematology tests will be listed only:

Red blood cells count (RBC)	White Blood Cells (WBC)	
Hemoglobin	Neutrophils (absolute value)	Neutrophils (%)
Hematocrit	Lymphocytes (absolute value)	Lymphocytes (%)
Platelets	Monocytes (absolute value)	Monocytes (%)
	Eosinophils (absolute value)	Eosinophils (%)
	Basophils (absolute value)	Basophils (%)

The “most extreme value” recorded, and the corresponding number of days to the most extreme value recorded, will be summarized descriptively for Grade 3 or 4 abnormalities. This will be limited to the following selected “parameters of interest”: hemoglobin, neutrophils and platelets for the “most extreme” is defined as the value of smallest magnitude. Additional parameters may be added to this analysis as appropriate.

The median number of days to ‘recovery’ (Section 8.10) in patients with Grade 3 or 4 abnormalities that worsened from baseline will be obtained from Kaplan-Meier estimates.

Shift tables showing changes in the NCI CTCAE grade from baseline to the worst grade recorded post-baseline are tabulated. Parameters with NCI CTCAE criteria defined bi-directionally have low value abnormalities represented by a negative sign so that they may be differentiated from high value abnormalities. If the NCI CTCAE criteria are uni-directional the negative sign is not used even if the criteria are defined to flag low value abnormalities.

The rate per 100 patient years (see Section 8.9 for the appropriate details) of Grade 3 or 4 abnormalities in hemoglobin (low), neutrophils, and platelets, along with the corresponding 95% Poisson CIs, will be summarized.

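### SAP 8.10 counts recovery from a Grade 3/4 laboratory abnormality only at Grade 2 or 1, which read literally omits a direct return to Grade 0; its censoring dates also outlast laboratory testing

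*SAP*

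**What the plan says.** SAP 8.10 runs the clock from the first record of a Grade 3 or 4 abnormality that is worse than baseline or has no baseline value "until the time (subsequent event) when CTCAE grade for this test is reduced to a value 2 or 1".

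The censoring sentence opens "If the test continues to demonstrate the same (or higher) CTCAE grade". For a test that does so up to the end of the study or death, "the duration is censored at either the end of the study or" death. No other date is given.

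SAP 11.6.1 (Hematology) uses the definition: the median number of days to recovery "in patients with Grade 3 or 4 abnormalities that worsened from baseline will be obtained from Kaplan-Meier estimates".

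SAP 11.6, describing the shift-table scale for two-directional tests, says "where Grade 0 will correspond to" values within the normal range. A normal result therefore has its own grade, and it is neither 1 nor 2.

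On testing, Protocol 10.1.10.1 says "Collect blood for hematological assessments at the following time points and when clinically indicated". The scheduled points are baseline, Cycle 1 Day 15, before dosing in each cycle from Cycle 2, End of Treatment and the 30-day safety visit. Protocol 10.2.8 lists what is done in survival follow-up. The list ends with "SAE collection only if the SAE is related to study medication" and contains no laboratory test.

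**The concern.** The first problem is the event. A patient who is at Grade 4 on one test and normal on the next has recovered, but the grade was not reduced to 2 or 1. That patient does not fit the censoring sentence either, because the test no longer shows Grade 3 or 4. If such a patient is left at risk, a true recovery is lost. If a later test happens to show Grade 1 or 2, the recovery is recorded at that later date. Either way the Kaplan-Meier median is pushed up.

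The second problem is smaller. Recovery can be seen only when blood is drawn, yet the censoring dates named can fall long after the last draw. SAP 8.6 ties end of study to the 384th death; Protocol 8.2 ties it to the last patient's safety follow-up. A patient who stops treatment at Grade 3/4 and is not tested again could stay in the risk set without any chance of contributing an event.

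At stake is how quickly this toxicity is reported to resolve. No efficacy result depends on it.

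**Working it through.** The plan states no figure for days to recovery, so there is nothing to reproduce. The check is a comparison of the text followed by an illustration.

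**Is a direct fall to Grade 0 plausible?**
- A cycle is 28 days (Protocol 9.2.1). From Cycle 1 Day 15 to Cycle 2 Day 1 (Day 29) is 29 − 15 = 14 days. After that, scheduled on-treatment tests are at least 28 days apart unless extra tests are clinically indicated. Intermediate grades can pass unseen.
- Protocol 9.2.4.3 says, for patients with decreased neutrophils or platelets, that "the next cycle of study treatment should not be started until the resumption criteria in Table 6 are met". Table 6 sets neutrophils at 1500/mm³ or more and platelets at 75,000/mm³ or more. The test that clears a patient for the next cycle is therefore taken after substantial recovery. The documents do not reproduce the CTCAE cut-offs, so I do not assign these values to a grade.
- Example of late dating: Grade 4 on Cycle 1 Day 15, Grade 0 on Cycle 2 Day 1, Grade 1 on an undelayed Cycle 3 Day 1. Recovery occurred by day 14; the literal rule records 14 + 28 = 42 days.

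**Who can go without a retest?**
- Patients who continue are tested before each cycle and, for neutrophils and platelets, must meet Table 6. They are largely protected.
- Among patients who stop, the End of Treatment visit is not required when the decision comes within 2 weeks of the last treatment visit (Protocol 10.2.6). The 30-day visit may become a phone call if the patient cannot return before new therapy (10.2.7). Repeat testing (12.2.2) and follow-up of unresolved AEs (12.1.1) may both end when another treatment starts. So the protocol permits some patients to have no scheduled retest.

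**Size, continuous illustration.** Let m be the median recovery time and q the share kept at risk with no countable recovery, whether from an uncounted Grade 0 or no retest. The documents give neither. Assume exponential recovery, m = 14 days, recovery time unrelated to being affected, and death or end of study well after the recovery times. Then S(t) = q + (1 − q)·2^(−t/m), and setting S = 0.5 gives

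reported median = m·log2[(1 − q)/(0.5 − q)].

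- q = 5%: 14·log2(0.95/0.45) = 15.1 days
- q = 10%: 14·log2(0.90/0.40) = 16.4 days
- q = 20%: 14·log2(0.80/0.30) = 19.8 days

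The increases are 1.1, 2.4 and 5.8 days. A simulation of the no-retest case (200,000 patients per run; assumed death median 5/0.70 = 7.14 months; assumed end of study at day 240) gave 15.1, 16.3 and 19.7 days. Censoring at the last test gave 13.9 to 14.0.

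**Size, visit-based illustration.** Suppose the abnormality is seen on Cycle 1 Day 15. The retest is at 14 days (Cycle 2 Day 1) or at the 30-day visit. With a last dose on Day 12, that visit is on Day 42, which is 42 − 15 = 27 days later. If a share p of countable patients has recovered by day 14 and the rest by day 27, the reported median is 14 when p(1 − q) ≥ 0.5 and 27 otherwise. It moves only when p lies between 0.5 and 0.5/(1 − q): up to 52.6% for q = 5%, 55.6% for 10% and 62.5% for 20%. Outside that band nothing changes.

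**What the true median is.** For uncounted Grade 0 recoveries it is 14 days under these assumptions, so the longer figure is an error. For untested patients it depends. If non-retest is unrelated to recovery it is 14 days. If those patients never recover, 15.1, 16.4 and 19.8 are correct, and censoring at the last test gives 14, too short by the same 1.1, 2.4 and 5.8 days.

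**The case against.** The strongest reply is that the rest of the rule is out of sight. SAP 11.6 ends by pointing to specific laboratory data rules whose location is redacted, and SAP 14 records an added Data Handling Guidance for safety endpoints, also redacted. A rule on Grade 0 or on lapsed testing could sit in either. This stands, and it limits the point to the wording of 8.10.

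The Grade 0 omission is probably a drafting slip, and a sensible programmer would read Grade 2 or lower. That is likely, but 8.10 is the visible definition and says otherwise. The correction costs one phrase.

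A reader might infer that 8.10 orders untested patients to be carried to death or end of study. It does not. Its trigger is a test that keeps showing Grade 3 or 4, and a patient with no later test does not meet it. Carrying such patients forward follows only from those being the only dates offered.

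The group without a retest is also narrow, for the reasons shown in the working, and a patient who dies early would leave the risk set at death. This stands too.

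Finally, last-test censoring is not clearly better: patients too ill to return may well be unrecovered. The SAP itself is mixed. It censors PFS and ECOG deterioration at the last assessment (3.2.2, 3.2.3.3) but QoL deterioration at end of study, cut-off or death (10.4.4.4.6). This is why the counts of untested patients and of their deaths are needed beside the median.

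**Conclusion.** The point holds, with the Grade 0 wording first and the censoring dates second. As written, 8.10 does not recognise a direct return to normal as recovery, and if such patients stay at risk the median is too long. If they were instead left out of the analysis, the direction would depend on how their recovery times compare with the others'. The text does not say which would happen.

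The censoring part is a gap with an uncertain direction. Patients whose last test is still Grade 3/4 may be kept at risk when recovery cannot be observed. Whether that distorts the median depends on whether they later recovered.

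The size is unknown and may be nil, since the documents give neither the share affected nor the recovery time. The increases of 1.1 to 5.8 days rest on an assumed 14-day median and an assumed 5% to 20% affected; under visit-based sampling the median often would not move.

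It would be tempting to conclude that the reported median is biased by a stated number of days, or that the trial's conclusions are weakened. The documents support neither. This is one descriptive safety summary; OS, PFS, alpha and power are untouched. It should be corrected because the correction is cheap.

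**What to change.** In SAP 8.10:

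1. Define recovery as the first later test of that parameter at CTCAE Grade 2 or lower, including Grade 0.
2. Censor patients without recovery at their last valid test of that parameter.
3. Beside the median, report by arm the number of patients with no retest and how many of them died.

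If the redacted laboratory rules already say this, a cross-reference from 8.10 is enough.

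The cost is two phrases, one derivation and one count by arm. The downside belongs to the second change: patients with no retest then contribute no follow-up, so the median can be too short if they are the sickest. The third change lets a reader judge that.
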